WHO	World Health Organization

1 OVERVIEW

This statistical analysis plan (SAP) provides a comprehensive and detailed description of strategy, rationale, and statistical techniques to be used to assess safety and efficacy in the 03-CL-1702 study of lucinactant for inhalation in preterm neonates. The purpose of the SAP is to ensure the credibility of the study findings by pre-specifying the statistical approaches to the analysis of study data prior to database lock. This SAP provides additional details concerning the statistical analyses that are outlined in the protocol.

Note: this study was terminated early due to business considerations and not as a result of any safety concern. As a result, only 12 subjects were enrolled. Thus, no statistics will be calculated in this study; only summary statistics will be computed and assessed.

1.1 Background

1.1.1 Treatment of Neonatal Respiratory Distress Syndrome

Respiratory distress syndrome (RDS) of the newborn is a disease that results from insufficiency of pulmonary surfactant in the immature neonatal lung, which occurs with high frequency in preterm infants and carries high morbidity and mortality, especially in very preterm infants. Exogenous surfactant treatment reduces mortality and morbidity in preterm infants with RDS (1,2). Intratracheal surfactant replacement therapy (SRT) has well-established benefits in infants with RDS and has become a standard, recommended therapy for this condition (3,4,5,6). Early SRT is more effective in reducing morbidity and mortality due to RDS than SRT delivered later (2), and multiple doses are sometimes necessary (1).

Intratracheal instillation of surfactant into the lung requires endotracheal intubation or insertion of a thin intratracheal catheter, often with concomitant positive pressure mechanical ventilation (MV). However, endotracheal intubation is an invasive, painful procedure that itself has potential deleterious effects to the infant, including hypoxemia, bradycardia, hypertension, increases in intracranial pressure and cerebral blood flow which may increase the risk of intraventricular hemorrhage (IVH) (7,8), and tracheal injury which may lead to the development of subglottic stenosis (9). Further, MV is associated with morbidities such as ventilator-associated lung injury and volutrauma/barotrauma resulting in air leak syndromes such as pneumothorax and/or pulmonary interstitial emphysema (PIE). MV may also contribute to development of chronic lung disease (CLD)/bronchopulmonary dysplasia (BPD) (10).

In order to avoid endotracheal intubation and MV in preterm neonates with mild-to-moderate RDS, a strategy of using nCPAP as an effective means of providing ventilatory support is now accepted

and recommended practice (3,4,5,6,11). nCPAP improves respiratory function in neonates by increasing functional residual capacity, improving lung compliance and dilating upper airway structures, thereby improving gas exchange and reducing work of breathing (11,12). Devices that generate and deliver nCPAP, as well as patient interfaces such as nasal prongs, have been specifically designed, manufactured, and made commercially available for use in neonates.

Studies in very preterm neonates of initial treatment of RDS with nCPAP alone (13,14,15,16), including meta-analyses (17,18), have shown outcomes with this approach that are similar to traditional, early treatment with intratracheal surfactant. These studies have consistently shown that in neonates treated with nCPAP, the need for surfactant therapy is less than that of neonates treated with intubation and SRT, and that the important outcome of death or bronchopulmonary dysplasia (BPD (defined as the need for oxygen [O₂] treatment at 36 weeks post-menstrual age [PMA]) is equal or less frequent with nCPAP. In neonates treated with nCPAP, approximately 33-67% of patients required intubation and intratracheal surfactant replacement, meaning that 1/3 to 2/3 of patients were able to avoid intubation altogether. Thus, the strategy of initially supporting neonates with nCPAP and reserving SRT only for those who require intubation appears to be reasonably effective and potentially safer by avoiding intubation. Two meta-analyses (10,19) and a systematic review (20) have suggested that use of nCPAP as the primary respiratory support modality in preterm neonates reduces the need for intubation and the rate of BPD, with a number need to treat (NNT) of 25 for BPD (10).

Older gestational age infants treated with nCPAP may be at higher risk of air leak than younger infants (21). In a cohort of 297 neonates 25-32 weeks gestation with RDS initially treated with nCPAP alone, 65 (22%) overall required intubation (“nCPAP failure”). The rate of nCPAP failure was 45% in the subgroup 25-28 weeks’ gestation, consistent with prior reports, where only 15% of infants 29-32 weeks’ gestation had nCPAP failure. Notably, the rate of pneumothorax prior to intubation was 10% in the younger cohort (also consistent with most prior reports) but was 23% in the older gestational age infants as a whole and 47% in those older infants who failed nCPAP.

1.1.2 Development of Aerosolized Device for Lucinactant Delivery

Windtree Therapeutics, Inc. (Windtree) has developed lucinactant for inhalation, an investigational drug-device combination product, to deliver aerosolized SRT to preterm neonates with RDS who are being supported with nCPAP. Lucinactant for inhalation (AEROSURF®) is comprised of a drug component, lyophilized lucinactant, and a device component, the Aerosol Delivery System (ADS). Lyophilized lucinactant is a lyophilized form of SURFAXIN® (lucinactant) Intratracheal Suspension, an exogenous SRT approved by the U.S. Food and Drug Administration (NDA 021746) (not currently marketed based solely on business considerations and not as the result of

any safety, efficacy, or quality concerns). The ADS device uses novel capillary-based aerosol generator technology to aerosolize reconstituted lucinactant, providing a high-density surfactant aerosol output with an appropriate particle size (2 to 4 microns mass median aerodynamic diameter [MMAD]) for respiration and deposition within the neonatal lung. The ADS may allow aerosolized lucinactant to be deposited in the lungs of preterm neonates in sufficient quantities to affect a therapeutic response analogous to that of endotracheal instillation of surfactant.

Data from a large neonatal database support the assumption that prophylactic use of aerosolized surfactant and nCPAP may reduce the need for intubation by 36% in neonates with a birth weight of 1001 to 1500 grams (22). Nonclinical studies using the CAG technology in preterm lambs have demonstrated that aerosolized lucinactant significantly improved lung mechanics and gas exchange compared with preterm lambs receiving CPAP alone (23). In parallel, pilot clinical studies in neonates with RDS (Study KL4-CPAP-01) (24) as well as in adults with asthma and cystic fibrosis (Study KL4-ASTH-01) have demonstrated that lucinactant aerosolized with commercially available nebulizers appears to be generally well-tolerated. The ADS represents the clinical version of the CAG technology, which is being used in clinical trials, to aerosolize lucinactant. This study will employ the next generation, commercially-equivalent, ADS.

The purpose of this study is to evaluate the safety and efficacy of lucinactant for inhalation used in conjunction with nCPAP, in comparison to nCPAP alone, in preterm neonates 26 to 32 completed weeks PMA with RDS.

1.2 Objectives

This study is designed to investigate the safety and efficacy of lucinactant for inhalation in preterm neonates 26 to 32 completed weeks (ie, $26^{0/7}$ to $32^{6/7}$ weeks) PMA. Efficacy and safety will be based on clinical evaluations. The endpoints specified are similar to those in Protocols 03-CL-1201, 03-CL-1401, and 03-CL-1202 to allow for qualitative comparisons.

The objectives of this study are to evaluate the safety and efficacy of lucinactant for inhalation delivered by the next generation ADS device in conjunction with nCPAP, in comparison to nCPAP alone, in preterm neonates with RDS, as assessed by the incidence of and time to respiratory failure due to RDS in the first 72 hours and through 28 days of life, oxygen saturation and use of supplemental oxygen, all-cause mortality through 28 days of life, the incidence of bronchopulmonary dysplasia (BPD) at 36 weeks PMA, and the duration of mechanical ventilation.

In addition, this study will evaluate the device performance and the ability to administer up to 3 lucinactant for inhalation repeat treatments. The efficacy estimate will be used to calculate the sample size for future studies.

1.2.1 Efficacy Objective

The primary estimand for this study is the occurrence of intubation for the purpose of mechanical ventilation or surfactant administration in preterm neonates 26 to 32 weeks PMA in the intent-to-treat (ITT) population (all randomized subjects). Intercurrent events include 1) treatment administration interruptions and 2) intubations for reasons other than MV or surfactant administration. Due to the small number of subjects as a result of the termination of the study, and that statistical testing will not be performed, intercurrent events will not be evaluated.

1.2.2 Primary Endpoint

The primary endpoint for this study is the number of subjects with respiratory failure due to RDS or all-cause death within the first 28 days of life. Respiratory failure due to RDS is defined as intubation (including intratracheal catheter placement) for MV and/or surfactant administration.

Subjects meeting the criteria of respiratory failure due to RDS must continue to be followed for all safety evaluations until the time the subject completes the study or withdraws.

1.2.3 Key Secondary Endpoints

The key secondary endpoints of this study include the evaluation of the following:

1. Respiratory failure due to RDS or death through 72 hours
2. Respiratory failure due to RDS through 72 hours and 28 days of life
3. Time to respiratory failure due to RDS or death through 72 hours and 28 days of life
4. BPD and survival without BPD at 36 weeks PMA
5. Severity of BPD at 36 weeks PMA
6. Oxygen saturation and use of supplemental oxygen

1.2.4 Other Secondary Endpoints

Other secondary endpoints of this study include the evaluation of the following:

1. Common complications of prematurity through 36 weeks PMA (IVH, periventricular leukomalacia [PVL], pulmonary hemorrhage, apnea, NEC, patent ductus arteriosus [PDA], acquired sepsis, ROP).
2. Duration of MV and oxygen requirement through 36 weeks PMA.
3. Changes in fraction of inspired oxygen (FiO₂), partial pressure of carbon dioxide (PCO₂), and oxygen saturation as measured by pulse oximetry (SpO₂).

4. Number/duration of and reason for re-hospitalization and urgent care visits through 12 months corrected age.
5. Respiratory medications through 12 months corrected age.

1.2.5 Safety Evaluations

The following safety measures are to be documented in the electronic case report form (eCRF) in accordance with timings outlined:

1. All-cause mortality through 28 days of life (date and time of death, if applicable)
2. AEs, including adverse device effects (ADEs) and AEs of special interest including AEs during the dosing period, complications related to placement of bi-nasal prongs, and air leak. AEs that are ongoing at 36 weeks PMA will be followed for an additional 30 days
3. Concomitant medications
4. Use of respiratory support and supplemental O₂, including the following:
 - a. Need for endotracheal intubation and MV
 - b. Mode of respiratory support, including oxygen only (without positive pressure)
5. Physical examinations
6. Assessments of the following:
 - a. Vital signs
 - b. O₂ saturation, as determined by pulse oximetry (SpO₂)
 - c. Chest radiography prior to intubation
7. Monitoring of PCO₂ and FiO₂

1.3 Hypotheses

Due to the fact that the study was terminated early, hypothesis testing and inferential statistics will not be used.

2 INVESTIGATIONAL PLAN

2.1 Study Population

This study population will be comprised of preterm neonates $26^{0/7}$ to $32^{6/7}$ completed weeks PMA who are receiving care in a NICU and are receiving nCPAP as the primary support modality for RDS. This study will enroll preterm neonates who are candidates for SRT and nCPAP.

Subjects will be enrolled by strata: subjects $26^{0/7}$ to $28^{6/7}$ weeks PMA and subjects $29^{0/7}$ to $32^{6/7}$ weeks PMA. The study population will be randomized in a 1:1 ratio into 1 of 2 treatment groups; however, the first 2 subjects at each site will receive open-label active treatment. Approximately 130 subjects (approximately 65 in the active group and 65 in the control group) were to be enrolled at 1 of approximately 10 study sites in the US, Poland, and China, and it is anticipated that approximately 720 subjects will be screened to meet the enrollment goal (8:1 ratio of screened to enrolled).

However, due to business considerations and not as a result of any safety concerns, study enrollment was terminated on 10 December after 12 subjects had been enrolled in Poland.

2.1.1 Inclusion criteria

Each subject must meet all of the following inclusion criteria to be enrolled in this study:

1. Signed ICF from legally authorized representative. Where allowed, it is recommended that consent is obtained antenatally.
2. Gestational age of $26^{0/7}$ to $32^{6/7}$ weeks PMA.
3. Successful implementation of non-invasive support or ventilation within 30 minutes of birth.
4. Spontaneous breathing.
5. Investigator determination of RDS. A chest x-ray should be obtained before treatment to confirm the diagnosis.
6. Within the first 6 hours after birth, requires an nCPAP of 5 to 7 cm H₂O that is clinically indicated for at least 15 minutes with an FiO₂ of ≥ 0.25 to ≤ 0.35 to maintain SpO₂ of 90% to 95%. Transient (< 5 minutes) FiO₂ excursions outside this range do not reset the time requirement.

2.1.2 Exclusion Criteria

Subjects meeting any of the following exclusion criteria may not be enrolled in this study:

1. A heart rate that cannot be stabilized above 100 bpm within 5 minutes of birth
2. Recurrent episodes of apnea requiring positive pressure ventilation (PPV) administered manually or mechanically through any patient interface
3. A 5-minute Apgar score < 5
4. Major congenital malformation(s) or craniofacial abnormalities that preclude the use of nCPAP, diagnosed antenatally or immediately after birth
5. Clinically significant diseases or conditions other than RDS which could potentially interfere with cardiopulmonary function (eg, congenital heart disease, hydrops fetalis or congenital infection)
6. A known or suspected chromosomal abnormality or syndrome
7. Premature rupture of membranes > 3 weeks
8. Hemodynamic instability requiring vasopressors or steroids for hemodynamic support and/or presumed clinical sepsis
9. A need for intubation and/or invasive MV at any time before enrollment into the study
10. The administration (or plan for administration) of any the following:
 - a) Another investigational agent or investigational medical device
 - b) Any other surfactant agent
 - c) Systemic corticosteroids (other than antenatal steroids)
11. Presence of air leak (pneumothorax, pneumomediastinum, pneumopericardium, subcutaneous emphysema, or definite evidence of PIE) on the baseline chest radiograph, or diagnosed via ultrasound or illumination.

2.2 Study Design and Randomization

This is a multinational, multicenter, randomized, double-blind (masked), controlled study to evaluate the safety and efficacy of lucinactant for inhalation in conjunction with nCPAP compared with nCPAP alone. Preterm neonates 26 to 32 completed weeks PMA who are being cared for in a neonatal intensive care unit (NICU) and who are within the first 8 hours after birth, who had successful implementation of noninvasive respiratory support within 60 minutes of birth, and who are candidates for SRT will be enrolled. The preferred initial mode of noninvasive support is study nCPAP; however, other modes are acceptable if the investigator feels it is safe to switch the subject to study nCPAP following consent and screening. There will be 2 phases in the study, a primary

phase through 36 weeks PMA and a longer-term follow-up phase through 1-year corrected age. Data analyses and presentations will be conducted after each phase.

Infants will be randomized into 1 of 2 parallel treatment groups, active (lucinactant for inhalation 160 mg TPL/kg) or control (nCPAP only), with 3 repeat doses allowed if repeat dose criteria are met. Repeat doses will be allowed no sooner than 20 minutes from completion of the previous dose and all repeat doses must be complete within 36 hours after randomization. Reconstituted lyophilized lucinactant (reconstituted with sterile water for injection) will be aerosolized by the investigational device, the Aerosol Delivery System (ADS), using the capillary aerosol generator and introduced into the nCPAP circuit. Those infants randomized to the control arm will receive nCPAP alone.

2.2.1 Treatment Groups

Randomization must occur within 6 hours of birth. Study treatment with lucinactant for inhalation must be initiated as soon as possible (within 2 hours of randomization), but no later than 8 hours after birth. For the first 2 subjects at each site and subjects randomized to the active study treatment group, the duration of the initial treatment is 100 minutes (corresponding to 160 mg TPL/kg). The subject will be connected to the study nCPAP and study airway connector. Following this change in the airway circuit, subjects will need to stabilize for at least 15 minutes before being connected to the ADS.

For sham treatment, no active drug will be prepared. Instead, the ADS will be prepared and delivered to the bedside in a masked manner. Masking will occur as with active treatment (eg, behind a curtain). The subject will be connected to the same setup as active subjects (using the study nCPAP and study airway connector). Subjects receiving sham will simulate being connected to nCPAP via the ADS but the ADS itself will not be powered on or connected. The start time for sham treatment (treatment initiation) will be the time at which this simulated connection occurs; the stop time will be 110 minutes later (to account for an approximate 10 minutes to switch the syringe and cartridge in the active treatment group). The subject will remain masked for the same duration as active subjects. As with the active treatment, if the subject's FiO₂ level is not at room air (0.21) by the end of the "treatment" time, the site should prepare and conduct a repeat "treatment"; each repeat treatment time will be 50 minutes. At the end of the assigned sham treatment time, the subject will be switched to clean nCPAP equipment (if necessary), as occurs at the end of active treatment. Masking equipment may then be removed.

Treatment Group	Study Assignment
160 mg/kg	Lucinactant for inhalation 160 mg TPL/kg (administered over 100 minutes) in conjunction with nCPAP (n = up to 35) Up to 3 repeat doses of 80 mg TPL/kg are to be given if repeat dosing criteria are met.
Control	nCPAP alone (sham treatment) for 110 minutes (n = up to 80) Up to 3 repeat sham treatments of 50 minutes are to be given if repeat dosing criteria are met.

Note: The first 2 subjects at each site will receive open-label active treatment. Masking procedures for the initial treatment will be followed for all repeat treatments in all treatment groups

Preterm neonates who successfully meet all eligibility criteria will be randomly assigned within their applicable stratum (26 to 28 completed weeks PMA or 29 to 32 completed weeks PMA) to one of the 2 treatment groups in a 1:1 ratio, following the first two open-label subjects at each site. Subjects will be randomized/enrolled using centralized allocation electronically (eg, interactive response technology [IRT]), including the open-label subjects (the first 2 subjects at each site). Neonates from multiple births will be randomized independently. Randomization information will be provided to the study drug preparer (eg, pharmacist). The PI, study staff (eg, site coordinator) (as applicable), and attending physicians as appropriate will be masked to the treatment assignment, as described in the site's blinding/masking plan. Infants who are randomized and on study nCPAP but no longer meet qualification criteria before treatment will still receive the study treatment, unless it is unsafe to do so in the opinion of the investigator.

If at any point during the delivery of lucinactant for inhalation a potential safety risk to the subject is identified, aerosolization must be discontinued and local NICU procedures followed to ensure the safety of the subject. Any significant clinical findings or observations must be documented and communicated to Windtree at the earliest time point possible.

2.2.2 Repeat Dosing

Up to 3 repeat doses will be allowed for each treatment group. The repeat doses will consist of 80 mg TPL/kg for the active group and 50 minutes of sham to the control group and will occur if repeat dosing criteria are met. The repeat dosing criterion is defined as 20 minutes from completion of the previous dose and the subject has a need for $\text{FiO}_2 > 0.21$ to maintain SpO_2 of 90% to 95%. The repeat treatment should occur as soon as possible after the 20-minute time period has elapsed, but no more than 1 hour after meeting criteria.

As with the initial dose, the randomization system will be used to receive the study drug assignments, and all other procedures that were performed for the initial dose will be followed for the administration of the repeat doses.

If, in the opinion of the PI, repeat dosing would compromise the safety of the subject, repeat dosing will not occur. If a subject qualifies for repeat dosing but does not receive repeat dosing, the reason for this will be documented.

2.2.3 Sample Size Justification

Given that this is an estimation study, it is not powered to achieve statistical significance; however, based on the results from previous studies, it will be sufficient to show a qualitative improvement for the active group.

The treatment difference (delta) between active and control treatments will be calculated for the primary and key secondary efficacy endpoints. The delta calculated will be used to plan additional studies and as supporting evidence of efficacy.

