WINDTREE THERAPEUTICS, INC.

Statistical Analysis Plan

A Multinational, Multicenter, Masked, Randomized, Parallel Group, Controlled Study to Assess the Safety and Efficacy of Lucinactant for Inhalation versus nCPAP Alone in Preterm Neonates 26 to 32 Weeks Gestational Age with Respiratory Distress Syndrome

Protocol Number: 03-CL-1702

Version 2.0 (Amendment 1)

SAP Version: 1.0

01 August 2021

**A Multinational, Multicenter, Masked, Randomized, Parallel Group, Controlled Study to
Assess the Safety and Efficacy of Lucinactant for Inhalation versus nCPAP Alone in
Preterm Neonates 26 to 32 Weeks Gestational Age with Respiratory Distress Syndrome**

Statistical Analysis Plan

Author/Project Biostatistician

[name]
Executive Director, Biostatistics and Data Management

Date

By signing below, I have read through the entire statistical analysis plan and agree to implement the plan.

[name]
Senior Vice President, Chief Medical Officer

Date

EXECUTIVE SUMMARY

The objectives of this study are to evaluate the safety and efficacy of lucinactant for inhalation delivered by the next generation ADS device in conjunction with nCPAP, in comparison to nCPAP alone, in preterm neonates with RDS, as assessed by the occurrence of and time to respiratory failure due to respiratory distress syndrome (RDS) or all-cause death in the first 72 hours and through 28 days of life, oxygen saturation and use of supplemental oxygen, the incidence and severity of bronchopulmonary dysplasia (BPD) at 36 weeks post-menstrual age (PMA), and the duration of mechanical ventilation. In addition, this study will evaluate the device performance and the ability to administer up to 3 lucinactant for inhalation repeat treatments.

This is a multinational, multicenter, randomized, double-blind (masked), controlled study in 26 to 32 completed weeks PMA preterm infants. Infants will be randomized into 1 of 2 parallel treatment groups, with 3 repeat doses allowed if repeat dose criteria are met. Reconstituted lyophilized lucinactant (reconstituted with sterile water for injection) will be aerosolized by the investigational device, the Aerosol Delivery System (ADS), using the capillary aerosol generator and introduced into the nCPAP circuit. Those infants randomized to the control arm will receive nCPAP alone.

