Exposure, defined as the emitted dose, is the amount of lucinactant that is delivered at the connection to the patient interface by the ADS at a constant rate of flow. The theoretical inhaled dose – the fraction of the aerosolized lucinactant that the infant is exposed to that is likely to be inhaled – is estimated by product of: 1) the aerosol concentration, 2) the minute ventilation of the infant, and 3) the administration time of the aerosol.

The first 2 infants enrolled at each site will receive open-label active treatment (lucinactant for inhalation); all subsequent infants will be randomized into the two masked treatment groups.

Treatment Group	Study Assignment
Lucinactant	Lucinactant for inhalation 160 mg TPL/kg (administered over 100 minutes) in conjunction with nCPAP (n = up to 35) Up to 3 repeat doses of 80 mg TPL/kg are to be given if repeat dosing criteria are met.
Control	nCPAP alone (sham treatment) for 110 minutes (n = up to 35) Up to 3 repeat sham treatments of 50 minutes are to be given if repeat dosing criteria are met.

Note: Masking procedures will be followed for all doses (initial and repeat).

Due to business considerations (and not as a result of safety concerns), enrollment for the study was terminated early on December 10, 2020. The last subject was enrolled on 27 November, 2020

and the last visit is expected on 19 January, 2021. A total of 12 subjects were enrolled. As a result, the planned analyses will be significantly curtailed and no statistical testing will be performed.

The independent data monitoring committee (DMC) was to evaluate the degree of risk involved in study participation and oversee the safety and welfare of study subjects. During the primary phase (all subjects have not yet completed 36 weeks PMA), the chair received regular reports on SAEs and AEs. The DMC was to have conducted 1 preplanned meeting after approximately 33% of subjects have been enrolled, which was cancelled.

Repeat dosing will be allowed up to 36 hours following randomization. Subjects meeting the repeat dosing criterion will receive up to 3 additional treatments of either 80 mg TPL/kg or sham treatment. The control subjects that meet the repeat dosing criteria must carry out all the procedures conducted for the active subjects to protect study blinding.

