4. Use of respiratory support and supplemental O₂, including the need for endotracheal intubation and MV and the mode of respiratory support, including oxygen only (without positive pressure)
5. Physical examinations
6. Assessments of vital signs, O₂ saturation, and chest radiography prior to intubation
7. Monitoring of PCO₂ and FiO₂

Follow-Up Period:

Due to the early termination of the study, assessments and analysis during the follow-up period were cancelled.

Analysis Populations:

The statistical analysis of both the primary and secondary objectives will be based on all enrolled preterm neonates. Due to the early termination of the study, all enrolled neonates that received any medication will be the only population analyzed. Since all randomized subjects received study treatment, this will be described as the ITT population for efficacy analyses and as the safety population for safety analyses; however, the populations will be the same.

For all efficacy assessments, only summary statistics without statistical testing will be utilized.

The treatment difference (delta) between active and control treatments will be calculated for the primary and key secondary efficacy endpoints. The delta calculated may be used to plan additional studies.

TABLE OF CONTENTS

EXECUTIVE SUMMARY	3
TABLE OF CONTENTS	6
ABBREVIATIONS.....	8
1 OVERVIEW.....	9
1.1 BACKGROUND.....	9
1.1.1 Treatment of Neonatal Respiratory Distress Syndrome	9
1.1.2 Development of Aerosolized Device for Lucinactant Delivery	10
1.2 OBJECTIVES	11
1.2.1 Efficacy Objective	12
1.2.2 Primary Endpoint	12
1.2.3 Key Secondary Endpoints	12
1.2.4 Other Secondary Endpoints	12
1.2.5 Safety Evaluations	13
1.3 HYPOTHESES.....	13
2 INVESTIGATIONAL PLAN	14
2.1 STUDY POPULATION	14
2.1.1 Inclusion criteria	14
2.1.2 Exclusion Criteria	15
2.2 STUDY DESIGN AND RANDOMIZATION.....	15
2.2.1 Treatment Groups	16
2.2.2 Repeat Dosing	17
2.2.3 Sample Size Justification	18
2.2.4 Study Schedule	19
3 STUDY SUBJECT CHARACTERISTICS	20
3.1 SUBJECT DISPOSITION	20
3.2 DEMOGRAPHICS AND BASELINE CHARACTERISTICS	20
3.2.1 Demographics	20
3.2.2 Medical, Birth and Maternal History	20
3.3 STUDY AND CONCOMITANT MEDICATION.....	21
3.3.1 Compliance	21
3.3.2 Number of Doses	21
3.3.3 Previous and Concomitant Medication	21
3.4 PROTOCOL VIOLATIONS/DEVIATIONS.....	21
4 EFFICACY ANALYSIS.....	21
4.1 EFFICACY POPULATIONS	22

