4.2 Statistical Analysis

All analyses will be performed for all subjects combined and by treatment group. Only summary statistics will be used.

All continuous variables (eg, birth weight, body temperature, PCO₂) will be summarized using number (n), mean, standard deviation (SD), median, 1st quartile, 3rd quartile, minimum, and maximum. All discrete variables (eg, sex, AEs, common complications of prematurity), will be summarized using frequency (n) and percent.

The treatment difference (delta) between active and control treatments will be calculated for the primary and secondary efficacy endpoints. The delta calculated may be used to plan additional studies and as supporting evidence of efficacy.

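### SAP 2.2.3 keeps, for 12 infants, a sufficiency sentence written beside up to 130, and offers as efficacy support a delta that has no interval and an unsettled population

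*SAP*

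**What the plan says.** Protocol 13.4 gives a total of up to 130 subjects, about half in each group. It then says that this is an estimation study, not powered for significance, but sufficient for a qualitative improvement given earlier results. SAP 2.2.3 repeats that statement word for word: "it will be sufficient to show a qualitative improvement for the active group".

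The SAP is dated "01 August 2021". Its Executive Summary says that enrolment was terminated on 10 December 2020 and that "A total of 12 subjects were enrolled"; sections 1 and 2.1 give the same number. Sections 1.3, 4 and 8.3 rule out hypothesis testing, and 4.2 limits the analysis to summary statistics.

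The SAP describes the use of delta in four places:
- 2.2.3: "The delta calculated will be used to plan additional studies and as supporting evidence of efficacy".
- 4.2: "The delta calculated may be used to plan additional studies and as supporting evidence of efficacy".
- Executive Summary, Analysis Populations: "The delta calculated may be used to plan additional studies", with no mention of efficacy support.
- 1.2: "The efficacy estimate will be used to calculate the sample size for future studies".

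On who is analysed, the Executive Summary says that "all enrolled neonates that received any medication will be the only population analyzed". SAP 4.1 bases efficacy on all enrolled infants and does not summarise the open-label infants (the first two at each site, all on active treatment) separately. Yet the Executive Summary says that only later infants are randomised to the masked groups, SAP 1.2.1 sets the estimand in all randomised subjects, and Protocol 13.2 says that open-label efficacy data will not be pooled.

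**The concern.** Other parts of the SAP were rewritten for the early stop: intercurrent events, hypotheses, subgroups and follow-up. Section 2.2.3 was not, and no other section withdraws or qualifies it. As it stands, the SAP asserts for 12 infants a property that was claimed for up to 130.

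The risk lies in how the estimate is described and reused. A difference without an interval could be reported as efficacy support, or used to size the next neonatal trial, when its direction says little and its size almost nothing. If open-label infants are counted, the active arm alone contains unmasked infants without concurrent randomised controls. Intubation is a clinician's decision, and Protocol 6.7 requires those who influence it to be masked, so this is a possible source of bias.

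**Working it through.** **Is there a figure to reproduce?** No. Neither document gives a power, effect size or precision target for 130, for 12, or for the leftover sizes (70 in Protocol 7 and 13.3; 35 per arm in parts of the SAP). The check therefore asks what the sentence could mean at each size.

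**Inputs**
- Failure rates: 32% active v 44% control (Protocol 2.3.2.3, Study 03-CL-1202 without interruptions); 27% v 53% (Protocol 3.2.3.5, Study 03-CL-1201, pooled 75 and 100 mg TPL/kg); 44% v 44% for no effect (Study 03-CL-1202, mITT).
- These are earlier nCPAP failure rates at other doses. They stand in for the 28-day composite.
- A qualitative improvement is not defined. It is read here as a lower observed failure rate on active.
- The split of the 12 is not given. With two open-label active infants per site and the rest 1:1, one site gives 5 v 5 masked (7 v 5 pooled), two sites 4 v 4 (8 v 4), three sites 3 v 3 (9 v 3).

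**Direction.** P(better) = sum of P(X = i) × P(Y = j) over all i/n_A < j/n_C, with X ~ Bin(n_A, p_A) and Y ~ Bin(n_C, p_C).

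Example, 3 v 3 at 32% v 44%: P(X = 0, 1, 2) = 0.314, 0.444, 0.209, and P(Y = 0, 1, 2, 3) = 0.176, 0.414, 0.325, 0.085. So P(better) = 0.314 × 0.824 + 0.444 × 0.410 + 0.209 × 0.085 = 0.259 + 0.182 + 0.018 = 0.459.

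**Precision.** The 95% Newcombe interval combines the two Wilson limits (l, u): lower = d − √[(p_A − l_A)² + (u_C − p_C)²], upper = d + √[(u_A − p_A)² + (p_C − l_C)²]. Its half-width was averaged over all outcomes at 32% v 44%.

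| Active v control | P(better), 32 v 44% | P(better), 27 v 53% | P(better), 44 v 44% | Expected 95% half-width (points) |
|---|---|---|---|---|
| 65 v 65 | 0.908 | 0.999 | 0.465 | 16.0 |
| 35 v 35 | 0.821 | 0.984 | 0.452 | 21.3 |
| 7 v 5 pooled | 0.645 | 0.809 | 0.486 | 42.6 |
| 8 v 4 pooled | 0.572 | 0.746 | 0.417 | 43.3 |
| 9 v 3 pooled | 0.569 | 0.730 | 0.429 | 44.9 |
| 5 v 5 masked | 0.531 | 0.710 | 0.376 | 44.9 |
| 4 v 4 masked | 0.499 | 0.665 | 0.362 | 48.1 |
| 3 v 3 masked | 0.459 | 0.608 | 0.342 | 52.2 |

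Where P(better) is low in the small equal splits, ties take much of the rest: at 5 v 5 and 32% v 44%, better 0.531, tie 0.236, worse 0.234.

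**One outcome.** Failures in 2/5 v 3/5 give d = −20 points. The Wilson limits are 0.118 to 0.769 and 0.231 to 0.882. Lower = −0.200 − √(0.282² + 0.282²) = −0.599; upper = −0.200 + √(0.369² + 0.369²) = +0.322. The interval runs from −60 to +32 points.

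**The case against.** The best reply is that the SAP already disarms the sentence. It states the termination, the 12 infants and the absence of testing, and no analysis or decision depends on 2.2.3. It also requires counts and percentages by group, so a reader sees the denominators. All of that is true, and there is no concealment. But dropping tests does not withdraw a claim of sufficiency or of efficacy support, and 1.2 and 2.2.3 say that the estimate will be used.

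A second reply is that intervals were deliberately left out, and that the protocol's statistical section promised none for delta even at 130. That makes the interval a recommendation and not a breach. It is still the natural companion to an estimate in a self-described estimation study.

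Some stronger readings are not supported:
- **That 12 infants are unlikely to show a lower rate on active.** On that reading the chance is roughly even at 32% v 44% and 61 to 81% at 27% v 53%. The weakness is that chance alone gives 34 to 49%. Improvement becomes unlikely only if it means an interval that excludes zero, and the sentence itself contrasts qualitative with statistical significance.
- **That the uncertainty is 55 points or more.** Wald half-widths at these sizes reach that, but the method is poor with so few infants. The Newcombe figures are 43 to 52.
- **That the comparison was 6 v 6, all randomised.** That conflicts with two open-label active infants at each site.
- **That delta certainly includes open-label infants.** SAP 4.1 says only that they are not summarised separately, whereas 6.1 says outright that safety data are pooled. The efficacy text permits inclusion but does not spell it out.

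**Conclusion.** The point holds as a defect of wording and definition that should be corrected before results are reported. SAP 2.2.3 is unrevised for 12 infants; 2.2.3 and 4.2 go further than the Executive Summary on efficacy support; delta has no precision measure; and its population conflicts with Protocol 13.2 and SAP 1.2.1.

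At 32% v 44%, the chance that active looks better falls from 91% at 65 per arm (82% at 35 per arm) to about 46 to 65%, against 34 to 49% with no true effect. At 27% v 53% it falls from 99.9% to about 61 to 81%. The expected 95% half-width rises from about 16 points to about 43 to 52.

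These figures rest on borrowed rates, on reading qualitative improvement as a lower observed rate, and on one to three sites with even masked splits. Neither the site count nor the split is documented, so the ranges are illustrations and not bounds.

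**What to change.** 1. SAP 2.2.3: delete the sufficiency sentence, or replace it with: *With 12 infants the treatment difference will be very imprecise and the study is not expected to show or exclude an improvement.*
2. SAP 2.2.3 and 4.2: delete the efficacy-support wording. Align 1.2 and 2.2.3 with the Executive Summary, so that delta may inform planning.
3. SAP Executive Summary (Analysis Populations) and 4.1: reconcile with Protocol 13.2, SAP 1.2.1 and the Executive Summary's account of who is randomised. Calculate delta in the masked randomised infants and list the open-label infants separately.
4. SAP 4.2: report the binary primary and key secondary deltas with counts and a 95% Newcombe or exact interval, labelled descriptive, without tests. Clarify 1.3 and 8.3 so that this is allowed.

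Protocol 13.4 needs no change. The cost is a few SAP edits and one interval per binary delta, with no new data. The wording becomes less favourable and the comparison smaller: 5 v 5 instead of 7 v 5 if there was one site. The lack of a BPD table and the title of Table 4.1 are separate points.
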